## List of abbreviations

Abbreviation	Meaning
BP	Blood pressure
ALT	Alanine aminotransferase
anti-HCV	Total antibodies to Hepatitis C Virus
AST	Aspartate aminotransferase
ATC	Anatomical-therapeutic-chemical classification
APTT	Activated partial thromboplastin time
VAS	Visual-analog scale
HIV	Human immunodeficiency virus
GGTP	Gamma-glutamyl transpeptidase
DEE	Confidence interval
CS	Clinical study
CRO	Contract research organization
MD	Medical device
GCP	Good clinical practice
NSAIDs	Non-steroidal anti-inflammatory drugs
IEC	Independent ethics committee
AE	Adverse event
OA	Osteoarthritis
PT	Prothrombin time
SAE	Serious adverse event
SOP	Standard operating procedure
ESR	Erythrocyte sedimentation rate
CRD	Chronic renal disease
RR	Respiration rate
HR	Heart rate
ALP	Alkaline phosphatase
eCRF	electronic Case Report Form
ACR	American College of Rheumatology
HBs-Ag	hepatitis B surface antigen

ICH	International council for harmonization of technical requirements for pharmaceuticals for human use
JSN	Joint space narrowing
JSW	Joint space width
MedDRA	Medical Dictionary for Regulatory Activities
OEI	Evaluation of the treatment effectiveness by the investigator
OEP	Evaluation of the treatment effectiveness by the patient
WOMAC	Western Ontario and McMaster Universities Osteoarthritis
WOMAC-A	Subscale of pain according to the osteoarthritis index developed by researchers at the Western Ontario and McMaster Universities Osteoarthritis
WOMAC-B	Subscale of stiffness according to the osteoarthritis index developed by researchers at the Western Ontario and McMaster Universities Osteoarthritis
WOMAC-C	Subscale of function according to the osteoarthritis index developed by researchers at the Western Ontario and McMaster Universities Osteoarthritis
WOMAC-T	Change in the total score on the scale of the osteoarthritis index, developed by the researchers at the Western Ontario and McMaster Universities Osteoarthritis

# Synopsis

## Name of the study

Survey Data Analysis to Assess the Long-term Efficacy and Safety of Intra-articular HBISA Endoprosthesis of Synovial Fluid (NOLTREX™) in Knee Osteoarthritis.

## Studied MD

HBISA endoprosthesis of synovial fluid NOLTREX™ (hereinafter referred to as NOLTREX™)

HBISA (polyacrylamide hydrogel, hereinafter - PAAG) is intended for the symptomatic treatment of adult patients with osteoarthritis (OA) reducing joint pain and improving mobility. The aim of the 1-year follow-up is to evaluate the long-term safety and efficacy of one and two intra-articular PAAG courses in patients with symptomatic Kellgren and Lawrence (KL) grade 2 and 3 knee OA.

## Duration of treatment:

### RCT (IA/PAAG-SI/OA/2019)

A course of two weekly intra-articular (IA) injections of 4.0 ml NOLTREX™ (2.5 + 1.5 ml, or 2.0 + 2.0 ml from two syringes through one needle [one injection]). The number of injections was determined by the doctor depending on the stage of knee OA and the clinical response. In order to avoid overfilling the joint with a dense, slowly resorbable material, with a good clinical result (a decrease in the severity of joint pain according to 100-mm VAS by more than 40% compared to the basal level), the course of injections was discontinued.

### OLE (IA/PAAG-SI/OA/2020)

A repeated course of NOLTREX™ IA injections was carried out after a re-evaluation of the feasibility and possibility of a repeated course of NOLTREX™ injections after 6 months, after 9 months and after 12 months after the start of the IA/PAAG-SI/OA/2019 study.

## Comparison MD

Not applicable

## The duration of the study, the number of research sites and patients

This study was 1-year follow-up involving patients with knee OA who received IA injections of NOLTREX™ in the RCT IA/PAAG-SI/OA/2019 (CS1) and OLE IA/PAAG-SI/OA/2020 (CS2). The follow-up data were collected through telephone interview (using questionnaire) conducted in April-July 2022, 12 months after the completion of OLE IA/PAAG-SI/OA/2020. Analysis included data collected at Visit 1 (week 1) of the parent study IA/PAAG-SI/OA/2019, visit 0 (screening) and Visit 5 (week 23) of OLE.

**Number of patients:**

The survey was conducted in a population that included 57 patients from RCT and OLE divided into 3 subgroups depending on the treatment they received: 30 patients (52.63%) received 2 courses of therapy; 17 patients (29.82%) received 1 course of therapy; 10 patients (17.54%) patients received placebo. The placebo group was very small for statistical assessment for most parameters and was not mainly analyzed in main part of them. That is why it is single arm study in comparation of 1 or 2 course of Noltrex (47 patients).

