1-year follow-up of a randomized controlled trial IA/PAAG-SI/OA/2019 with open-label extension IA/PAAG-SI/OA/2020 to assess the long-term efficacy and safety of Intra-articular HBISA Endoprostheses of Synovial Fluid NOLTREX™ in patients with symptomatic Kellgren and Lawrence (KL) grade 2 and 3 knee OA.

The duration of the study, the number of research centers and patients

This study was 1-year follow-up involving patients with knee OA who received IA injections of NOLTREX™ in the RCT IA/PAAG-SI/OA/2019 (CS1) and OLE IA/PAAG-SI/OA/2020 (CS2). The follow-up data were collected through telephone interview (using questionnaire) conducted in April-July 2022, 12 months after the completion of OLE IA/PAAG-SI/OA/2020. Analysis included data collected at Visit 1 (week 1) of the parent study IA/PAAG-SI/OA/2019, visit 0 (screening) and Visit 5 (week 23) of OLE.

Number of patients:

In the current study (CS3) including patients who met inclusion criteria and had no exclusion criteria who received MD NOLTREX™ in the CS1 (IA/PAAG-SI/OA/2019) and/or CS2 (IA/ PAAG-SI/OA/2020) study and also participated in CS3. Therefore, a formal sample size calculation was not performed.

The survey was conducted in a population that included 57 patients, divided into 3 subgroups depending on the treatment they received: 30 patients (52.63%) received 2 courses of therapy; 17 patients (29.82%) received 1 course of therapy; 10 patients (17.54%) patients received placebo. The placebo group was very small for statistical assessment for most parameters and was not mainly analyzed in main part of them. That is why it is single arm study in comparation of 1 or 2 course of Noltrex (47 patients).

Purpose of research

The aim of 1-year follow-up is to evaluate the long-term safety and efficacy of a single or repeated course of IA NOLTREX™ in patients with symptomatic Kellgren and Lawrence (KL) grade 2 and 3 knee OA.

Study design and methodology:

The 1-year follow-up study involved patients with knee OA who had received a course of IA injections of NOLTREX™ or placebo in the RCT IA/PAAG-SI/OA/2019 and OLE IA/PAAG-SI/OA/2020. The follow-up data were collected during a telephone interview/questionnaire conducted in April–July 2022 – 12 months after the completion of OLE. Analysis included data collected at Visit 1 (week 1) of the parent study IA/PAAG-SI/OA/2019, visit 0 (screening) and Visit 5 (week 23) of OLE.

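### The one-course result 12 months after the extension rests, by implication, on the 17 of 47 surveyed NOLTREX patients who were not re-treated, so it is conditioned on a post-treatment event

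*Protocol*

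**What the plan says.** The Protocol (Studied MD) sets out to "evaluate the long-term safety and efficacy of one and two intra-articular PAAG courses". The SAP (Purpose of research) sets out to "evaluate the long-term safety and efficacy of a single or repeated course of IA NOLTREX™". Both therefore pose a question about one course as well as about two.

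The Protocol (Number of patients) describes "57 patients from RCT and OLE divided into 3 subgroups depending on the treatment they received", and gives "30 patients (52.63%) received 2 courses of therapy; 17 patients (29.82%) received 1 course of therapy" and "10 patients (17.54%) patients received placebo". The placebo patients are mostly set aside: "That is why it is single arm study in comparation of 1 or 2 course of Noltrex (47 patients"). The SAP repeats these counts.

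On how the second course came about, the Protocol section on the OLE says it was given "after a re-evaluation of the feasibility and possibility of a repeated course of NOLTREX™ injections after 6 months, after 9 months and after 12 months", counted from the start of CS1. Entry to CS2 required at least one NOLTREX injection in CS1, completion of CS1 Visit 5, and consent (Study design and methodology, both documents).

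The primary and secondary outcomes in both documents are WOMAC and VAS changes to 12 months after CS2. None counts or times the second course. Both documents say there is no hypothesis and that results are descriptive. The Protocol section on demographic, baseline and follow-up data nevertheless compares the subgroups by ANOVA or Kruskal–Wallis.

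**The concern.** Because CS2 entry required NOLTREX in CS1, all 47 NOLTREX patients had a first course in CS1. Whether a patient counts as 'one course' or 'two courses' was settled months later, by a re-evaluation and by consent. The label is a consequence of what happened after treatment, not something assigned at the start.

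The 17 could include patients who still had benefit, patients judged unsuitable for repetition, and patients who did not enter CS2. The documents do not separate these. A mean change in the 17 describes patients who ended up without a second course. It does not tell a reader what to expect after being given one course. The 30 re-treated patients also carry information on the first course, yet no planned endpoint uses it before re-treatment.

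At stake is one of the study's two stated questions. The contrast of 17 with 30 has the same fault, and would be read as the added value of a second course.

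**Working it through.** **1. The plan's own figures.** The inputs are the counts in Number of patients (both documents).
- 30/57 = 52.63%, 17/57 = 29.82%, 10/57 = 17.54%.
- 30 + 17 + 10 = 57, and 30 + 17 = 47.

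All reproduce. There is no sample size or power figure to check; the SAP says no formal calculation was done.

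**2. Who informs the one-course answer.** Set three statements side by side: groups are formed by treatment received; the second course belongs to CS2; all endpoints are set 12 months after CS2. At that time the 30 have had two courses. Only the 17 remain to represent one course: 17/47 = 36.2%. The other 30/47 = 63.8% leave that answer because of an event after the first course.

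**3. Interval for the re-treated proportion.** Wilson 95% interval with p = 30/47 = 0.6383, n = 47 and z² = 3.8415:
- centre = (p + z²/2n)/(1 + z²/n) = (0.6383 + 0.0409)/1.0817 = 0.628
- half-width = 1.96 × √(p(1−p)/n + z²/4n²)/1.0817 = 1.96 × √(0.00491 + 0.00043)/1.0817 = 0.132
- interval = 49.5% to 76.0% (exact method: 48.5% to 77.3%)

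This applies to surveyed patients only.

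**4. How large selection could be (illustration only).** Assume that the 17 are exactly those with the best status at the decision, and that this status has correlation ρ with the later score. The values of ρ are assumed; the documents give none. The mean of the 17 then differs from the mean of all 47, had none been re-treated, by ρ × φ(z)/p. Here p = 17/47, z = −0.354 and φ(z) = 0.3747, so the multiplier is 0.3747/0.3617 = 1.036.

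| ρ | Shift in the 17 (SD) |
|---|---|
| 0.1 | 0.10 |
| 0.3 | 0.31 |
| 0.5 | 0.52 |
| 0.7 | 0.73 |

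The 95% CI half-width for a mean at n = 17 is t(0.975, 16)/√17 = 0.51 SD. At ρ = 0.5 the shift is as large as that half-width. If the 17 were instead the patients with the worst status, the sign reverses. Perfect sorting is an extreme case, so the table shows a possible scale and does not estimate the bias.

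**5. Is there an unselected first-course time point?** CS1 Visit 5 (25 weeks) had to be completed before CS2 entry, and both documents list its completion under the inclusion conditions. It therefore precedes any second course and should exist for all 47. It is not among the visits listed for analysis, which are CS1 Visit 1, CS2 Visit 0 and CS2 Visit 5.

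**The case against.** The strongest reply is that the plan claims little. It states no hypothesis, presents descriptive results, and says openly that groups follow the treatment received. The endpoints name no subgroup, and no sentence says that one-course efficacy is estimated in the 17. This stands as far as wording goes: the reading is an inference from the grouping and the endpoint timing. It does not remove the problem, because a descriptive mean in a group formed by a later event is still selected, and the stated aim still asks about one course.

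Four stronger readings are tempting, and the documents do not support them.
- **That the one-course result is too favourable.** No reasons for the absence of a second course are given, so the bias could go either way.
- **That re-treatment shows how long one course lasted.** The OLE section speaks of feasibility and possibility, and CS2 needed consent. Nothing says that loss of benefit triggered the second course.
- **That re-treatment goes unreported.** The 30 and 17 are printed with percentages of 57. What is missing is the timing, the denominator of 47 and an interval.
- **That the 47 are an unselected first-course cohort.** They are patients who took part in the 2022 survey, after the re-treatment decision. The number given NOLTREX in CS1 is not stated separately from the 72 in that trial.

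It would also be wrong to take each patient's last value before a second course as the first-course outcome, because the re-treatment decision would then set the length of follow-up. Finally, the physician questionnaire covers treatment after leaving the studies, so nothing shows that reasons for having no second course were recorded.

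**Conclusion.** The point holds as a limit on interpretation. The survey result in the 17 (36% of 47) is conditioned on not being re-treated, and the contrast with the 30 is not randomised. Neither estimates the long-term effect of one course or the added effect of a second. The direction and size of the bias cannot be determined from the documents.

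The conclusion rests on two readings: that the subgroups by courses received are how the one-course aim is answered, and that the 17 and 30 were separated by the CS2 re-evaluation and entry process. A related gap follows from the 'and/or' wording on parent-study participation. Any of the 17 who never entered CS2 would lack CS2 Visit 0 and Visit 5, two of the three reference values of the primary outcome. The plan does not say whether there are such patients.

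The data remain usable, but as labelled they do not answer one of the two stated questions. The change should be made.

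**What to change.** Amend the Protocol (Number of patients; Primary and Secondary Outcome Measures; Analysis of demographic, baseline, and follow-up data) and the matching SAP text.

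1. Label the 17 'patients not re-treated' and the 30 'patients re-treated'. State that neither the result in the 17 nor the contrast between the groups estimates the long-term effect of one course or the added effect of a second.
2. Add the first-course WOMAC and VAS change from CS1 Visit 1 to CS1 Visit 5 (week 25), in all surveyed NOLTREX patients and by later re-treatment status. Describe it as a medium-term result. Where CS1 records allow, give it also for all NOLTREX patients treated in CS1. Add CS1 Visit 5 to the list of analysed visits.
3. Report the number and timing of second courses descriptively with a 95% CI, labelled 'among surveyed patients' (30/47 = 64%, Wilson 50% to 76%) and, where records allow, among all CS1 NOLTREX patients. Do not interpret it as duration of effect.
4. Tabulate reasons for no second course only if they were recorded, with a 'not recorded' category.

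The cost is some wording and a few tables. Items 2 and 3 depend on access to CS1 and CS2 records. The long-term claim for one course becomes narrower.

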**Purpose of the study**

1-year follow-up of a randomized controlled trial IA/PAAG-SI/OA/2019 with open-label extension IA/PAAG-SI/OA/2020 to assess the long-term efficacy and safety of Intra-articular HBISA Endoprostheses of Synovial Fluid NOLTREX™ in patients with symptomatic Kellgren and Lawrence (KL) grade 2 and 3 knee OA.

**Study design and methodology:**

The 1-year follow-up study involved patients with knee OA who had received a course of IA injections of NOLTREX™ or placebo in the RCT IA/PAAG-SI/OA/2019 and OLE IA/PAAG- SI/OA/2020. The follow-up data were collected during a telephone interview/questionnaire conducted in April–July 2022 – 12 months after the completion of OLE. Analysis included data collected at Visit 1 (week 1) of the parent study IA/PAAG-SI/OA/2019, visit 0 (screening) and Visit 5 (week 23) of OLE.

The multicenter, double-blind, randomized, comparative, placebo-controlled trial of the efficacy and safety of IA NOLTREX™ in the treatment of knee OA IA/PAAG-SI/OA/2019 (CS1) involved 72 patients over 50 years of age with a verified diagnosis of gonarthrosis in accordance with the criteria of the American College of Rheumatology (ACR) II-III radiographic stage according to the Kellgren-Lawrence classification. These patients received 1 to 2 injections (at an interval of 1 week) of MI NOLTREX™ into the most affected (target) knee joint.

The OLE IA/PAAG-SI/OA/2020 (CS2) included patients who had received at least one intra- articular injection of NOLTREX™ in the RCT, completed Visit 5 and signed an informed consent form for participation in OLE.

This study aimed to assess the long-term efficacy and safety of IA NOLTREX™ based on data from CS1, CS2 and the results of a telephone interview/questionnaire for patients conducted in April-July 2022. The survey/questionnaire was conducted according to the following scheme:

1. Patient survey - current pain status on a visual analogue scale (VAS) and 3 questions about treatment after completion of the study, which is filled in from the patient's words.

2. Questionnaire for the physician about treatment after completion of the study, which is filled in by collecting the history of the disease and the methods of treatment used after exiting the study(s), from medical records, a medical information storage system (if applicable).

3. The Osteoarthritis Index questionnaire, developed by employees of the University of Western Ontario and McMaster Universities Osteoarthritis (WOMAC) for completion from the patient's words - identical to that previously used in the clinical studies of the MI "BVISA endoprosthesis of synovial fluid NOLTREX" under two study protocols: CS1 and CS2.

Since the WOMAC osteoarthritis index and VAS pain scores are similar to those used in CS1 and CS2, the aim of this study was to jointly analyze the data obtained in CS1, CS2, and the survey/questionnaire.

#### **Diagnosis and main inclusion criteria:**

Current study included patients who had previously participated in the IA/PAAG-SI/OA/2020 and/or IA/PAAG-SI/OA/2019 studies with the following conditions: 1. completion of participation in the clinical study IA/PAAG-SI/OA/2019 in the NOLTREX™ medical device group with the completion of visit 5 procedures (25 weeks):

#### **Inclusion criteria for the IA/PAAG-SI/OA/2019 (CS1) study**

1. Men and women over 50 years old;
2. Verified gonarthrosis according to the ACR criteria (knee pain in combination with one of the following signs: age over 50 years, crepitus in the joint or morning stiffness in the joint lasting less than 30 minutes in combination with radiographic signs of gonarthrosis);
3. II-III radiographic stage of gonarthrosis according to the Kellgren-Lawrence classification with predominant damage to the medial tibiofemoral region of the knee joint;
4. Radiographic joint space width (JSW) of the target knee joint of at least 2.5 mm.

#### **Inclusion criteria for the IA/PAAG-SI/OA/2020 (CS2) study**

1. Men and women over 50 years of age;
2. Signed informed consent form by the study participant;
3. Verified gonarthrosis according to the ACR criteria (knee pain in combination with one of the following: age over 50 years, crepitus in the joint or morning stiffness in the joint lasting less than 30 minutes in combination with radiographic signs of gonarthrosis);
4. II-III radiographic stage of gonarthrosis according to the Kellgren-Lawrence classification with predominant damage to the medial tibiofemoral region of the knee joint

**Evaluation criteria:****Efficacy:**

The integral assessment of efficacy was based on the statistical analysis of the main efficacy parameters.

**The efficacy of the study MD was assessed by the following endpoints.**

**Primary Outcome Measure(s):**

1. Change in the total WOMAC score (WOMAC-T) 12 months after completion of CS2 compared with the baseline value at Visit 0 (screening) of the IA/PAAG-SI/OA/2020 study, compared with the baseline value at Visit 1 (week 1) of the IA/PAAG-SI/OA/2019 study and the last value at Visit 5 (week 23) of the IA/PAAG-SI/OA/2020 study;

**Secondary Outcome Measure(s):**

2. Change in the WOMAC Pain (WOMAC-A) Score 12 months after completion of CS2 compared to the baseline value at Visit 0 (screening) of the CS2 study, compared to the baseline value at Visit 1 (week 1) of the IA/PAAG-SI/OA/2019 study and the last value at Visit 5 (week 23) of the CS2 study;
3. Change in the WOMAC Stiffness (WOMAC-B) score 12 months after completion of CS2 compared to the baseline value at Visit 0 (screening) of the CS2 study, compared to the baseline value at Visit 1 (week 1) of the IA/PAAG-SI/OA/2019 study and the last value at Visit 5 (week 23) of the CS2 study;
4. Change in the WOMAC Physical Function (WOMAC-C) Score 12 months after completion of CS2 compared with the baseline value at Visit 0 (screening) of the CS 2 study, compared with the baseline value at Visit 1 (week 1) of the CS1 study and the last value at Visit 5 (week 23) of the CS2 study;
5. Change in the 100-mm VAS Pain Score 12 months after completion of CI2 compared with the baseline value at Visit 0 (screening) of the IA/PAAG-SI/OA/2020 study, compared with the baseline value at Visit 1 (week 1) of the CS1 study and the latest value at Visit 5 (week 23) of the CS2 study;

**Safety:**

The current CS 3 assesses safety using medical absolute and relative contraindications for repeated intra-articular treatment, as well as physician-reported data, including information on pain medication use.

**Statistical methods:**

Statistical analysis was performed using the R statistical software package (R: A language and environment for statistical computing. R Core Team. R Foundation for Statistical Computing, Vienna, Austria. URL <https://www.R-project.org/> ) version 4.x.x, using package version control adapted and validated by Microsoft (Microsoft R Open. Microsoft and R Core Team. Microsoft, Redmond, Washington. URL <https://mran.microsoft.com/> ) using "A Guidance Document for the Use of R in Regulated Clinical Trial Environments" (<https://www.r-project.org/doc/R-FDA.pdf> ).

Statistical analysis was performed for data on all patients who participated in the study in accordance with the definitions of the populations for the analysis.

All available patient data were used for the analysis; due to the lack of a statistical hypothesis and the planned statistical analysis of any parameters, only the results of the descriptive analysis are presented.

Demographic, efficacy, and safety data were presented using descriptive statistics:

Continuous (quantitative) data were presented using the following parameters:

- Number of observations (n);
- Arithmetic mean (M);
- Standard deviation (SD);
- 95% confidence interval for the mean (95% CI);
- Minimum value (min);
- Maximum value (max);
- Median (Me);
- Interquartile range (ICR).

For variables presented as qualitative and ordinal indicators, absolute (n) and relative (%) frequencies for each category, as well as 95% CI, were calculated.

